Evening “Deep Dives” into ACT and CBT. For each of the first 16 evenings, the app will display a more in-depth lesson/exercise for participants in the JITAI group. The display time will have been selected by the participant during the issuing of the smartphone. The participant can “snooze” the “Deep Dive” (reschedule it for later in the evening), but has to read/do it on the scheduled evening. The “Deep Dives” (shown in Appendix B), which should each take approximately 5-15 minutes, will underscore and complement the general teaching on the introductory video. The intention is to provide skill training and philosophical context that will increase the value of the brief daily ACT and CBT messages. “Deep Dives” will alternate nightly between ACT and CBT and will be presented in the same order for all participants. The presentation of lessons in standardized sequence is typical for mobile interventions that include instructional modules. By giving the Deep Dives in the same order for everyone, we can present them more coherently. We think of the 16-night Deep Dive period almost as a psychological analog of a buprenorphine-induction period: at the end of it, every participant will have been titrated up to our targeted “dosage” of concept teaching and skill teaching.

We drew the material for the CBT “Deep Dives” from publicly available sources (such as the NIDA online “toolbox”); we drew the material for the ACT “Deep Dives” from publicly available sources and from a workbook by [name] (Hayes & Smith, 2005).

We will encourage participants to read/do the “Deep Dives” as scheduled, and we will discharge participants who have not done all 16 within the first 21 nights. That is, we will permit (but not encourage) up to five missed nights, and when a night is missed, the “Deep Dives” will resume with the missed material, adding one night to the total length of presentation.

The “Pull” Period. Participants in the JITAI group who complete the 7-week push period will immediately continue to the 1-week pull period. The pull period will be a superimposition of pull upon of push: push messages and assessments will continue as before, mostly because we want to continue collecting full daily data on every participant. But participants will also be able to initiate (pull) the “Deep Dives” they have already read/done, or view messages as

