- Participants will be encouraged to and assisted in transferring to a community treatment program for continuation of care. Participants who do not wish to transfer to continued treatment in the community will be tapered from buprenorphine at Archway over 5 weeks with an optional additional 2 weeks if needed to secure transfer or to treat opioid withdrawal symptoms and minimize chances of relapse. At any time during the taper, participants can choose to transfer to another program.
- Transfer of care/continuity of care – Throughout the study, counselors will be engaged with participants about plans for care/treatment/counseling following discharge from the study (i.e., aftercare). Aftercare, of some kind, is always recommended. For those participants who continue to use illicit drugs or who relapse to use, community-based methadone and/or buprenorphine programs are recommended. Participants will be given a list of treatment programs and must initiate the contact. Archway staff will supply the transfer summary and help to coordinate a transfer date. Depending on the participants' input and status, a drug-free counseling center or Narcotics Anonymous (NA) may also be recommended. Throughout their time at Archway, participants have access to lists of alternative and aftercare programs, private MDs as well as applications for financial support, subsidized healthcare, health insurance, job and housing opportunities, etc.
- Due to clinical considerations, taper procedures can occasionally alter the total number

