If the participant is receiving OBOT at Archway, he or she will have a 21-day medication taper and be assisted into transferring to community-based treatment..

Mishaps (lost or damaged smartphones).

Participants who lose or damage their smartphone during the study may be issued another one. (“Damage” is defined as anything that renders the smartphone permanently unusable for study purposes, including a cracked screen.) A second mishap will lead to discharge with a 21-day taper.

At the end of week 10, participants will return the smartphone to us. If this is their first issued smartphone and it is not damaged (as defined above), they may choose to keep it or return it for \$300. If this is their second issued smartphone and it is not damaged (as defined above), they may choose to keep it or return it for \$100.

Prior to the start of buprenorphine taper, OBOT participants will have the following choices: (a) to remain in the study through the taper phase, or (b) to transfer to another program.

Other procedural issues

Continuation of participants who have been hospitalized or incarcerated during the study: At any given time, it can be expected that several participants will be either hospitalized or incarcerated for short periods. If those participants return to the program immediately after their release, we will re-admit them to Archway after they are medically evaluated to resume. This can result in participants being in treatment for more than 16 weeks.

Because circumstances vary greatly across participants, we have chosen not to adopt a rigid cutoff for the maximum time a patient's participation can be delayed in this way. In the past, our informal cutoff has typically been about two weeks.

During a participant's incarceration, we will follow NIDA IRP procedures regarding research on prisoners: no data will be collected from the participant, and he or she will not be contacted by NIDA IRP staff or Archway staff. However, the participant will be permitted to inform Archway staff that he or she is incarcerated. After the participant is released, he or she will be permitted and encouraged to contact NIDA IRP staff or Archway staff and ask to be continued in the study. We will then decide whether to reactivate the participant, based on scientific and medical criteria.

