Collection of data from incarcerated participants will not be an issue, because, like other personal property, the devices will be routinely confiscated by prison authorities upon entry and not returned until the prisoner is released. If the devices are returned to us and they somehow do contain data from time during incarceration, we will delete those data.

On some occasions, initiation of mobile data collection will begin later than scheduled. This typically occurs when the participant cannot meet with the experimenter at the appropriate time to receive the necessary introduction to the experimental condition. In all cases, all data collection will start as close as possible to the protocol schedule.

A 21-day taper will be offered to OBOT participants who choose to withdraw voluntarily from the study. Participants will also be discharged (with a 21-day taper for OBOT participants) if they meet one or more of the following termination criteria: (1) missing 4 (OBOT) or 3 (TE) study visits; (2) on 6 occasions, bringing in a dead smartphone following a missed clinic visit; (3) violating clinic rules; (4) failing to comply with smartphone data collection; or (5) losing or damaging two smartphones. In some cases, where disruptive behavior is a risk to staff or other participants, the OBOT taper may be less than 21 days. Any taper, whether administrative or voluntary, will include take-homes for Saturdays and Sundays.

H. Collection and storage of human specimens or data

Electronic data will be stored on the NIDA IRP's secure, password-protected system of electronic medical records (Clinical Data Warehouse; CDW). Paper records are stored in the Archway clinic under double lock in an area where individuals who are not part of the study staff do not have access (BRC building; room number 01B605). After the study is completed and data have been analyzed, the paper records will be stored at an NIH-approved commercial facility for the storage of sensitive data until approval for their disposal has been given.

Audio from the formative interviews will be sent without identifiers to a HIPAA-compliant professional transcription service. These services typically transcribe medical records. We will not permit the service to keep or share data. We will keep the transcripts indefinitely on secured servers. The audio will be accessible only to investigators and will be deleted when all interview data have been summarized—most likely within a year.

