Pregnancy will not be a criterion for exclusion or discharge. We arrived at this decision after intensive discussion of the issue with the NIDA IRB during its initial review of the protocol. Buprenorphine maintenance is beneficial for pregnant women with opioid dependence and for their fetuses (Johnson et al., 2003). EMA monitoring is not considered risky for pregnant women or their fetuses and has not been an exclusion criterion for our prior or current EMA studies. For the JITAI intervention, our reasoning is as follows, based on subparts a-j of 45 CFR 46.204. (a) Studies of JITAIIs in at least a thousand women, with or without substance-use disorders (e.g., Heron & Smyth, 2010; Free et al., 2011; Gustafson et al., 2014; Shrier et al., 2014; Muuraiskangas et al., 2015; Tufts et al., 2015), have not suggested any

effects that would increase risk to pregnant women or fetuses. (b) Any risk to fetuses from a woman's use of the JITAI app is not greater than minimal, and the purpose of this protocol is the development of important biomedical knowledge that cannot be obtained by any other means than a microrandomized study in a relevant, representative sample. (c) The protocol minimizes any risk that is associated with the JITAI. (d) Informed consent will be obtained from any pregnant woman who enrolls. (e) Not applicable (benefit is not solely to the fetus). (f) If any information arises on reasonably foreseeable risks to fetuses from a JITAI, participants will be informed. (g) No pregnant children will be enrolled. (h) No inducements will be offered to terminate a pregnancy. (i) No one involved in the research will have any part in decisions about termination of pregnancy. (j) No one involved in the research will have any part in decisions about the viability of a neonate.

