A. Parameters monitored: Because each patient is to be seen at Archway three days a week, any events can be readily noted: nurses routinely ask patients if they are experiencing any new health problems and record all adverse events. Under our current system, the nurses make weekly entries into NIDA/IRP's Clinical Data Warehouse (CDW, a Microsoft SQL Server database) including patient identifying information, the nature of the problem, date reported, date of onset, expectedness, seriousness, relatedness to the intervention, action taken, and outcome; the MAI can update and clarify this information, but cannot delete it.

Periodically, the MAI reviews the adverse-events information, noting any trends and reporting them to the IRB as appropriate. Patients' weight will be measured once per month; other vital signs may be taken to assess changes in participants' clinical condition. As part of usual Archway procedures, we routinely collect data on attendance, urine-test results, opioid-withdrawal symptoms, other subjective and psychological effects, and requests for dose

changes. The physician will review all lab results and make referrals and recommendations as appropriate.

B. Criteria for individual subject withdrawal/termination

Nonmedical criteria for termination. Participants will be discontinued from the study if they: (1) miss 4 study visits (OBOT) or miss 3 visits (TE, no taper as these participants do not receive treatment at Archway); (2) violate clinic rules; 3) fail to comply with EMA data collection; or (4) lose or damage two smartphones. Participants receiving OBOT from us will be offered a 21-day taper and assisted in finding a treatment provider in the community.

Participants receiving OBOT from us will be discontinued from the study possibly without a taper if they miss 3 consecutive scheduled visits.

Participants will be discontinued from the study (possibly with a taper of less than 21 days, which might not be at Archway) if they: (1) are rude and/or disruptive to the staff or to other patients; (2) try to buy or sell drugs on clinic or hospital property; (3) deface or damage clinic property; (4) try to tamper with a urine sample (for instance, by bringing urine from home, or by adding something to the urine).

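### The 21-day taper after discharge for a phone, data-entry or lesson failure has no stated exception for pregnant participants treated with buprenorphine by the study

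*Combined protocol and SAP*

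**What the plan says.** Section L.3 says that pregnancy neither bars entry nor causes discharge, and gives as one reason that "Buprenorphine maintenance is beneficial for pregnant women with opioid dependence and for their fetuses". Its point-by-point argument under the federal regulation concerns the app and does not discuss tapering or loss of medication.

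Four non-clinical rules can end participation for an OBOT participant:

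- **Second lost or damaged phone.** Section G, Mishaps: "A second mishap will lead to discharge with a 21-day taper". The rule recurs in Section G, Other procedural issues, and in Section L.5.B.
- **Dead phones.** Section G, Other procedural issues: "on 6 occasions, bringing in a dead smartphone following a missed clinic visit".
- **Smartphone data non-compliance.** Section G, Compliance with EMA and JITAI, makes a participant eligible for discharge after a second consecutive week below 82%. Other procedural issues and Section L.5.B word it as mandatory.
- **Unfinished Deep Dives (JITAI group only).** Section E.3: "we will discharge participants who have not done all 16 within the first 21 nights". For an OBOT participant Section G adds that "he or she will have a 21-day medication taper and be assisted into transferring to community-based treatment".

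Other procedural issues opens its list of termination criteria with "Participants will also be discharged (with a 21-day taper for OBOT participants". Section L.5.B is softer: "Participants receiving OBOT from us will be offered a 21-day taper and assisted in finding a treatment provider in the community".

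The optional taper at the end of the study lasts 5 weeks, "with an optional additional 2 weeks if needed to secure transfer or to treat opioid withdrawal symptoms and minimize chances of relapse".

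**The concern.** The protocol counts maintenance as a benefit to mother and fetus when it justifies inclusion. Read literally, its discharge rules then start a dose reduction in the same woman because of a phone, a data-entry shortfall or an unread lesson, with no clinical reason. Section L.4 states that participants withdrawn from buprenorphine will have withdrawal symptoms, eased by the gradual taper.

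Pregnancy is discussed only in Section L.3. The buprenorphine-risk text in L.4 and the termination text in L.5 do not mention it, and the screening measures listed in L.2 name no pregnancy test. Staff applying a discharge rule therefore have no instruction, and might not know that the question arises.

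At stake is continuity of treatment for a pregnant participant whose transfer to a community provider is not complete when the taper ends. The documents do not say how often transfer takes longer than 21 days.

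**Working it through.** **1. The one figure behind a trigger.** Section G says that five missed entries out of about 28 a week is 82.1% compliance. (28 − 5)/28 = 0.821, which agrees. Six missed gives 22/28 = 78.6%, below the 82% threshold.

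**2. What could stop the taper.** Each general safeguard, set against the four rules:

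| Safeguard | Where | Does it hold an administrative taper in pregnancy? |
|---|---|---|
| Help with transfer | G, L.5.B | Helps, but sets no condition on the taper; G has the participant make the first contact |
| Aftercare planning during the study | G, transfer of care | Lets planning start before discharge; guarantees no date |
| Dose adjustment on clinical judgment | L.4 | Permissive; not tied to discharge |
| Taper described as offered | L.5.B | The participant is still discontinued; the alternative named is help finding a provider, not continued dosing |
| Physician may hold or slow a taper, adding up to 2 weeks | G, weeks 12-16 | Written for the end-of-study taper and based on withdrawal signs and cravings |

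None mentions pregnancy, and none makes the taper wait for a confirmed transfer. If the physician's power were read across to the administrative taper, it would give at most 21 + 14 = 35 days.

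**3. Taper lengths.** The end-of-study taper is 5 × 7 = 35 days, or 7 × 7 = 49 with the extension. The administrative taper is 21 days: 21/35 = 60% and 21/49 = 43% of those lengths.

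**4. Rough numbers.** Inputs: enrollment ceiling 150 and completer target 85 (Section J); about half OBOT (L.2); 40% women (Précis); a dropout rate above 50% pauses enrollment (Section P). The pregnancy rate is my assumption, shown at 0, 5 and 10%; eligible ages are 18 to 75. Women and non-completion are assumed to be spread evenly over treatment sources and groups.

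- OBOT women: 150 × 0.5 × 0.40 = 30.
- Planned non-completion: 1 − 85/150 = 0.433, so 30 × 0.433 = 13. At 50%: 15.
- Pregnant among 13: 0, 0.65, 1.3. Among 15: 0, 0.75, 1.5.
- The Deep Dive rule reaches only the JITAI share: 30 × 50/85 = 17.6, about 18 women.

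These are planning figures, not bounds. They count non-completion from any cause and are not reduced for the share due to these four rules or for transfers completed in time.

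**5. Extra dosing if the taper is held to the end of week 11.** Phones are issued for week 3.

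- Second mishap in week 3: 11 − 3 = 8 weeks.
- Data non-compliance in weeks 3 and 4: 11 − 4 = 7 weeks.
- Deep Dives unfinished at night 21 (end of week 5): 11 − 5 = 6 weeks.

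**The case against.** The strongest reply is that the record is incomplete and the safeguards are real. Consent pages and appendices were not supplied. Section L.4 defers to institutional medical policies, and L.3 reports close discussion of pregnancy with the ethics board. A provision may exist there. That stands, and it limits the point to the supplied text.

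Second, the protocol softens the rules. A first lost phone may be replaced, low compliance brings a reminder first, and aftercare is discussed during the whole study, so transfer need not begin on the first day of the taper. This also stands. It lowers the chance of a gap but does not remove it.

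Third, Section S classes the Deep Dives as treatment-related, so that trigger is not purely a research task. Correct; it is still not a medical reason to stop buprenorphine.

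Fourth, no taper in the protocol waits for a confirmed transfer. The end-of-study taper only allows a capped extension, and a fully compliant pregnant woman faces the same taper-or-transfer choice at week 12. This is the best argument against giving the point much weight. The contrast with the end-of-study taper is one of length and flexibility, and any fix limited to the four rules only postpones the question.

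A reader might infer that the protocol contradicts itself or breaches the federal regulation it cites. The documents do not support either. Including pregnant women and having general discharge rules are compatible, and what is absent is a rule joining them. Nor do they support a claim of fetal harm beyond loss of the benefit that L.3 names.

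**Conclusion.** The point holds as a gap in participant protection, not as a statistical error. On the supplied text, four non-clinical criteria lead to discharge with a 21-day taper for any OBOT participant, and nothing says what happens if she is pregnant. The safeguards reduce the risk without clearly stopping the taper.

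The number affected is probably 0 to 1 and may be zero. This rests on ceiling enrollment, an even spread of women and dropout, and an assumed pregnancy rate. It would be wrong to read 1.5 as an expected count of women harmed: it uses all-cause non-completion at the highest rate shown, and harm also requires that transfer fails within the taper. Participants treated elsewhere are unaffected, because the study does not dose them. No estimate, error rate or sample size depends on the point. It is worth correcting because the change is cheap and the benefit at risk is one on which the protocol itself relies.

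**What to change.** Add to the discharge text in Section G (Compliance with EMA and JITAI, Mishaps, Other procedural issues) and in Section L.5.B:

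- Before any taper triggered by a second phone mishap, six dead-phone occasions, smartphone data non-compliance or unfinished Deep Dives, OBOT women are asked about pregnancy.
- If pregnant, the participant stops JITAI/EMA procedures. The taper is held, and buprenorphine continues at the usual clinic visits until transfer to a community provider is confirmed or the week-12 options apply, whichever comes first, unless the physician judges a taper clinically indicated.
- She counts as a non-completer under the dropout definition in Section P. State whether her later urine results enter the mixed model for opioid use in Section I.2, Hypothesis 3.

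Cite the rule in Section L.3 beside the sentence on maintenance. If a provision already exists in another document, a cross-reference there is enough. Leave the missed-visit, conduct and medical discharge rules unchanged: doses are delivered at visits, so attendance bears on safe dosing.

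The cost is one amendment, one question, and at most about 6 to 8 weeks of dosing, already planned for compliant participants, for probably 0 to 1 women. Randomization and sample size do not change. The rule postpones loss of maintenance; it does not secure treatment after week 12.
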